4.1. Study setting/context

Organizations and community-based associations working with socio-economically vulnerable women will be invited to participate. These organizations will be randomly allocated to invite women to either arm 2 or arm 3.

We aim to link the information sessions of the acceptability study to group activities that are offered by the organizations. This was suggested by the community health workers during the focus group discussions as a good way to motivate women to participate. It was reported that it is difficult to gather women for the sole purpose of an information session about their health (especially about cervical cancer that is often not known) and that linking it to an activity for which they are gathered will increase the participation rate.

We are paying attention that organisations and their catchment areas are not too close to each other to avoid spillover.

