4.2. Inclusion criteria

4.2.1. Participants

Women who are in a socio-economically vulnerable situation and therefore visit one of the abovementioned organizations. Women from the abovementioned hard-to-reach communities will be invited. They are eligible for inclusion if they meet the following criteria:

- are between the ages of 25 to 65 years of age, in line with the European Guidelines for initiating and stopping cervical cancer screening
- (ever been) sexually active;
- not diagnosed or in treatment for cervical cancer;
- not having had a hysterectomy
- not being pregnant
- Speaking the local language

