4.2.2. Community-based researchers offering the interventions

We aim to organize each session including team members with different and complementing backgrounds (medical – social/community – background knowledge specific to the organization). More particularly, we aim that each session is attended by at least 3 team members corresponding with one of each of the following profiles:

- 1) *A researcher with a medical background.* The interventions will be guided by the main researcher in charge of the acceptability study in each study country. The main researcher will take the lead during the educational sessions (arm 2 and 3), give the instructions about self-sampling (arm 3) and will be responsible for the management of the samples (arm 3). The main researcher will be assisted by fellow researchers involved in ELEVATE, including medical students (in the broad sense, including students studying medicine, health promotion, biomedical sciences, etc.). We expect that it will not be feasible for this main researcher to conduct all sessions. Therefore, the main researcher might be replaced by another health care professional (e.g. nurse, physician, medical assistant) or one of the medical students, after they were properly trained and followed some other sessions.

2) *Community-based researchers* will mainly include social workers and community (health) workers. They might not have a medical background but are experienced with working with hard-to-reach women. Community-based researchers will be involved in all stages of this study; however, their core responsibilities will be participant recruitment, assisting during the educational sessions, assisting during self-sampling and (post) counselling, and data collection (questionnaires). They will also be invited to participate in evaluation components of the pilot study (*Obj 6*). Community-based researchers can also help determine which wording will be used for recruitment and data collection.

It is estimated that 3-5 community-based researchers will be required in total.

The general criteria for the selection of community-based researchers include:

- Community and/or social workers experienced in working with socio-economically vulnerable women
- Ages between 21 and 60 (preferably 21-35 years old)
- Speak fluidly the local language
- Extra asset: Speak another language spoken by the target group
- Have communication, research and leadership skills
- Have a good relation with the community

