4.3. Recruitment of participants

In agreement with the participating organizations, the research team (including the community-based researchers) will hand out invitations (leaflets) to invite women to informative sessions on cervical cancer screening. While handing the invitation, the researcher will shortly describe the goal of the session, emphasizing the benefits for the women. If women are invited for arm 3, they will also be told that they will be offered a self-screening test during the session. Women will receive a leaflet stating the time and place they are expected. Women will be asked to invite other women as well.

We aim to link the sessions to group activities where women are already gathered such as sport activities, integration programs and meals in social restaurants. Therefore, we will work closely with the social

workers and volunteers active in the organizations and will ask for their support to invite women. However, we expect that their contribution will be limited due to their day-to-day workload and tasks.

We will explore with the respective organizations what the best approach is in their context with regard to the timeframe between the invitation and the information session. We learned during the focus group discussions that for many socio-economically vulnerable women it is difficult to commit to show up on another day, for various reasons. Therefore, we aim to organize the educational sessions directly following their group activity, integration class or meal in the restaurant (i.e. the moment they will be invited). In some subgroups of women, such as young mothers, it seems advisable to inform them that they will need to stay a bit longer so they can organize this.

All participants will be offered a small incentive for study participation, such as a voucher.

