5.2.1. Participation registers

Participation registers will be used during the pilot to keep track of the participation rate (*obj 1*).

$$\textit{Participation rate} = \frac{\textit{number of women who participate}}{\textit{number of women who were invited}}$$

The number of women who are invited will be defined by the number of leaflets (invitation letters handed out).

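### Inviters know the organisation's arm and the protocol does not exclude selective inviting, yet the leaflets they hand out are the denominator for the Objective 1 comparison of attendance

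*Protocol*

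**What the plan says.** Allocation is by organisation and comes first (Protocol 4.1): "These organizations will be randomly allocated to invite women to either arm 2 or arm 3". Inviting follows (4.3): "the research team (including the community-based researchers) will hand out invitations (leaflets) to invite women to informative sessions on cervical cancer screening". The invitation itself differs by arm (4.3): "If women are invited for arm 3, they will also be told that they will be offered a self-screening test during the session".

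Community-based researchers both recruit and help to deliver the intervention. Under 4.2.2, "their core responsibilities will be participant recruitment, assisting during the educational sessions, assisting during self-sampling" are among their duties. Staff and volunteers of the organisations may also help; the team "will ask for their support to invite women" (4.3), though it expects this help to be limited.

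On whom to invite, 4.2.1 says only: "Women from the abovementioned hard-to-reach communities will be invited". Section 4.3 links sessions to activities where women are already gathered and leaves the interval between invitation and session to be settled with each organisation. It adds: "Women will be asked to invite other women as well".

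Section 5.2.1 divides women who participate by women invited, and fixes the latter thus: "The number of women who are invited will be defined by the number of leaflets (invitation letters handed out". Hypothesis 1.1 (3.2) expects this rate to be higher in arm 3 than in arm 2.

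**The concern.** Randomising organisations balances the women available to be invited, apart from chance differences between organisations. It gives no protection against a difference that arises afterwards, when someone who knows the arm decides who gets a leaflet. Here that step also sets the denominator of an outcome: a woman who is passed over leaves no trace in the participation rate.

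No bad faith is needed. An inviter in arm 3 might skip women who seem unlikely to accept a self-test, which would raise the arm 3 rate. An inviter might equally approach reluctant women more readily because a test is on offer, which would lower it.

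The analysis could not undo this for attendance. The questionnaires in 5.2.2 go to participants only, and section 5.2 plans no data on women who were not invited or who were invited and did not come. How women are recruited belongs in the protocol, so an unseen SAP would not settle the matter.

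**Working it through.** The protocol gives no attendance rate, effect size or number to be invited, so there is no figure of its own to reproduce. Every rate below is an assumption and shows only what the mechanism can do.

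**1. False gain in attendance.** Let 100 suitable women be present in each arm, with true attendance of 50% in both. In arm 3 only, *s* women whose attendance would be *r* are passed over. The rate per leaflet is then (50 − *s*·*r*)/(100 − *s*).

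| *s* | *r* | Arm 3 rate | False difference |
|---|---|---|---|
| 10 | 30% | 47/90 = 52.2% | +2.2 points |
| 20 | 20% | 46/80 = 57.5% | +7.5 points |
| 30 | 10% | 47/70 = 67.1% | +17.1 points |

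If the same selection took place in arm 2 only, each sign would be reversed.

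**2. Masking a true gain.** Suppose keen women attend at 70% and reluctant women at 30% in arm 2, invited half and half: 0.5 × 70% + 0.5 × 30% = 50%. In arm 3 the offer adds 10 points in each group (80% and 40%). The keen share among women invited in arm 3 then decides what is seen:

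- 50% keen: 60%, a gain of 10 points (the truth)
- 40% keen: 0.4 × 80% + 0.6 × 40% = 56%, a gain of 6
- 30% keen: 0.3 × 80% + 0.7 × 40% = 52%, a gain of 2
- 25% keen: 0.25 × 80% + 0.75 × 40% = 50%, no gain

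**3. Indirect effect on take-up.** Section 6.1 measures take-up in arms 2 and 3 after the session, so leaflets are not its denominator. Keep attendance at 70% and 30% in both arms, and let true take-up among attendees be 80% (keen) and 40% (reluctant) in both arms.

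- Arm 2, 50% keen: (0.5 × 0.7 × 0.8 + 0.5 × 0.3 × 0.4)/0.50 = 0.34/0.50 = 68%
- Arm 3, 60% keen: 0.384/0.54 = 71%
- Arm 3, 70% keen: 0.428/0.58 = 74%
- Arm 3, 80% keen: 0.472/0.62 = 76%

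The false gain is 3 to 8 points before any adjustment for baseline differences among attendees.

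**4. Peer invitations.** The protocol does not say that women invited by other women receive a counted leaflet. With 100 leaflets and 50 attenders, 5, 10 or 20 further attenders without a leaflet give 55/100, 60/100 or 70/100, although attendance among women given leaflets is still 50%.

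**5. Would a headcount help?** Take *s* = 20 and *r* = 20% again, with passed-over women not attending. A headcount denominator gives 46/100 = 46%, and leaflets divided by women present gives 80/100 = 80%. Passing women over no longer raises the rate, and it becomes visible. It still lowers the rate by 4 points, so the headcount needs an invite-all rule beside it.

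**The case against.** **Discretion is not stated.** A reader might infer that the researchers choose whom to invite. No section says so. Sessions are tied to activities where women are already gathered, and inviting everyone present is a natural reading of 4.3. This stands: what the text supports is that selective inviting is not excluded. If inviting everyone is the intention, writing it down costs almost nothing.

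**Take-up is a different matter.** A reader might also infer that the leaflet count distorts the primary endpoint directly. It does not. Take-up is measured among attendees, and 5.2.2.1 collects screening history, willingness, acceptance of self-sampling and socio-demographics at the start of each session in both arms. Imbalance among attendees would be visible and partly adjustable. This also stands, and it limits the direct problem to Objective 1, which is not the primary endpoint.

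**Common habits cancel.** Section 4.2.2 expects only 3 to 5 community-based researchers. If the same people recruit in both arms, their shared habits largely drop out of the comparison. That is fair for habits unrelated to arm. It does not cover selection prompted by the arm 3 message itself.

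**The size is assumed.** This is true. The 17.1-point case needs inviters to pick out 30 women who attend at 10% while the other 70 attend at 67.1%, in one arm only.

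**A headcount has its own weaknesses.** It is made by eye by people who know the arm, it is unclear when activities recur or invitations come earlier, and it does not deal with peer-invited women. Section 9.1 also asks for privacy during invitations. These are reasons to specify the headcount carefully; they do not rescue the leaflet count.

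**Conclusion.** The concern holds for Objective 1. Allocation precedes invitation, inviters know the arm, no rule fixes who is invited, and the number of leaflets these people hand out is the denominator of a comparison between arms. Differential inviting could create or mask a difference in attendance under Hypothesis 1.1, and the planned data could not correct it.

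For arm 2 v arm 3 take-up the effect could only be indirect, through the mix of attendees, with partial adjustment possible.

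Neither size nor direction can be derived from the protocol. The 7.5-point example and the range of 2.2 to 17.1 points rest wholly on assumed attendance and assumed selection in one arm. The documents do not show that selective inviting is planned or will occur. The sponsor should close the gap because it is cheap to close before recruitment and cannot be repaired afterwards.

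**What to change.** - **Section 4.3:** require that, at each activity where invitations are made, every woman who appears to be of eligible age is offered a leaflet, in both arms, by the same procedure and without selection by the inviter. Arrange this within the privacy requirement of 9.1.
- **Section 5.2.1:** record in the participation register the number of such women present at the inviting activity, counting each woman once if the activity recurs or the invitation precedes the session day. Use this number as the denominator for Hypothesis 1.1.
- **Check on equal inviting:** report leaflets divided by women present, by arm.
- **Peer invitations:** record attendees invited only by other women separately, and leave them out of the numerator of this rate.

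The cost is protocol wording and one headcount per inviting activity in a register that already exists; no extra staff are needed. The downside is that age is judged by eye by staff who know the arm. Some ineligible women will enter the denominator, and the rate will be slightly lower.

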5.2.2. Questionnaires

5.2.2.1. *Self-administered questionnaire: knowledge, willingness and uptake of conventional screening (arm 2 and arm 3)*

A self-administered questionnaire will be applied to all participants at the start of each session to assess their current knowledge, willingness to get screened (conventionally) and uptake (*Obj 2*). Through this questionnaire, also socio-demographics, sexual behaviour and pregnancy history will be collected, as well as barriers of accessing cervical cancer screening.

Knowledge will be assessed through verifying whether the participant 1) has heard of cervical cancer, 2) knows the human papillomavirus (HPV) as primary cause, and 3) knows HPV is an STI.

Uptake of conventional screening will be assessed by asking participants' screening history, including 1) lifetime screening, 2) age at first screening and number of pap smears received, and 3) being screened in the last 3 years.

Participants will be asked to indicate their willingness to receive a pap smear and reasons for opting/not opting for conventional screening (reasons for interest/disinterest in continuation among those with previous pap smear uptake). Participants will also be asked to indicate acceptance of self-sampling. (See Appendix I: questionnaire 1)

5.2.2.2. *Self-administered questionnaire: attitudes towards self-sampling (arm 3)*

A self-administered questionnaire will be applied to all participants in arm 3 after the educational session, and before self-sample taking, to assess attitudes regarding self-sampling (pre-intervention) (*Obj 3*).

Attitudes will be assessed through asking participants to use 5-point Likert scale responses to indicate their perceptions of self-sampling and reasons for accepting or not-accepting the self-sample device. (See Appendix II: questionnaire 2)

5.2.2.3. *Self-administered questionnaire: users' perspectives in self-sampling (arm 3)*

A self-administered questionnaire will be applied to all participants in arm 3 who took a self-sample to assess users' experience regarding self-sampling (post-intervention) (*Obj 3*).

Users' perspectives will be assessed through asking participants to use 5-point Likert scale responses report their experience with the self-sampling brush. (See Appendix III: questionnaire 3)

5.2.2.4. *Follow-up questionnaire: knowledge, willingness and uptake of conventional screening (arm 2 and arm 3)*

A questionnaire will be applied during a follow-up phone call 3 months after the session to assess whether or not a screening appointment was made and participants got screened (=uptake), as well as to evaluate

knowledge after receiving the informative session (*Obj 2, Obj 4 and Obj 5*). (See Appendix IV: questionnaire 4)

Knowledge and willingness to get screened will be assessed by applying short, closed questions in order to quickly evaluate these outcomes by phone.

Women will be contacted through a message, phone call or e-mail (according to their preference) asking them when would be convenient for them to answer some questions. Women will be contacted up to 5 times maximum before considering them lost-to-follow.

Each participant will be attributed a unique identifier alpha-numeric code that will be used to link the respective questionnaires and to ensure pseudonymization of the data. The information that links the unique identifier code to the name and contacts of the participants will be registered. Only the community-based researcher (healthcare professional or community health worker) responsible for the data collection will have access to these personal data. No other member of the research team will have access to the name and contacts of the participants.

5.3. Focus group discussions

FGDs will be conducted with community-based researchers to explore their beliefs and attitudes towards the HPV screening strategy (including self-sampling) and understand their acceptance of the HPV screening intervention (*Obj 6*). One FGD will focus on arm 2, i.e. the feasibility of the educational session, and another FGD will be organized to discuss the implementation of arm 3. (See Appendix V: Topic guide)

The Conceptual Framework of Rogers' Diffusion of Innovation Model (1995) will be used to explore the topics related to characteristics of innovation (relative advantage, compatibility, complexity, trialability, observability).

6. Data analysis – sample size calculation

6.1. Quantitative data

The primary endpoint is the participation in screening which is defined in Arm 1 as the proportion of women who had a PAP smear taken by a GP or gynaecologist within the national screening program, in Arm 2 as the proportion of women who go for PAP smear after attending the information session with targeted referrals for off-site screening and in Arm 3 as the proportion of women who accept to take an HPV self-test on site after the information session.

Two important measures of take-up will be estimated:

Take-up 1 - To compare the take-up of an on-site HPV screening intervention with the current national screening services accounting for self-selection of women who decide to attend clinics (arm 1 vs. arm 3).

Take-up 2 - To compare the take-up of an on-site HPV screening intervention with targeted referrals to off-site screening (population impact regardless of self-selection) (arm 2 vs. arm 3).

Sample calculation was defined according to an estimated increase in take-up compared with current screening coverage for each study country.

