3.1. Study design

A 3-arm prospective acceptability study will be conducted with the following study arms:

Arm 1 – Assessment of screening coverage

Information about the screening coverage rates will be collected, focusing in particular on screening uptake among hard-to-reach women. The screening rates will be collected prior to the start of the study to avoid any contamination, i.e. uptake of screening that may occur through community mobilisation.

Outcome measures that will be examined for arm 1 are:

- Screening coverage at national level
- Screening coverage at local level/in hard-to-reach communities
- Follow-up rate among women who test positive (i.e., have a positive pap smear)

Arm 2 – Information session and follow-up assessment

In arm 2, a community-based researcher will educate women about sexual health and cervical cancer by using the materials that will be developed by the ELEVATE team. Women will be informed about cervical cancer screening (pap smear) and about where they can obtain these services off-site (health facilities); they will receive a contact number to make an appointment as well as information on how to reach the place of the consultation.

Outcome measures that will be examined for arm 2 are:

- Participation rate (i.e., women invited/women who attend the session)
- Knowledge, willingness and uptake of cervical cancer screening prior to the session
- Acceptability of self-sampling
- Uptake of cervical cancer screening through standard services: A 3-month follow-up by phone is proposed to check:

- whether the woman made an appointment; if no appointment was made, we will ask why; if an appointment was made, we will ask if she was able to attend the appointment
- Knowledge of as well as willingness to get screened for cervical cancer screening will also be assessed during the follow-up phone call
- Feasibility

Arm 3 – Information session and self-sampling

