3.2. Specific objectives

Objective 1: Assess and compare **attendance rates** following invitation to participate to the study

Hypothesis 1.1: Attendance will be higher when women are offered self-sampling compared to when women are only offered an educational session.

Objective 2: Evaluate the current **knowledge, willingness and uptake** of cervical cancer screening among participants of the acceptability study (arm 2 & 3); assess knowledge improvement and willingness to get screened 3 months after the intervention

Hypothesis 2.1: Knowledge and willingness to get screened will be poor and uptake of cervical cancer screening among the participants will be lower than the national average (but similar to results found in arm 1)

Hypothesis 2.2: After the information sessions, women will be able to link cervical cancer with HPV and will understand the benefit of screening; willingness to be screened will have increased

Objective 3: Assess **attitudes towards and users' experiences** of the HPV self-sampling test among hard-to-reach women (i.e. participants in arm 3)

Hypothesis 3.1: Attitudes towards on-site HPV self-sampling will be overall positive

Hypothesis 3.2: Women who use the self-sampling tool will have positive users' experiences related to the self-sampling device.

Objective 4: Compare the uptake of the on-site HPV testing (arm3) with the current national screening services (arm1) and with off-site referrals (arm2)

Hypothesis 4.1: Uptake of on-site HPV self-sampling will result in an increase in screening coverage compared to standard practices. (arm 3 vs arm 1)

Hypothesis 4.2: On-site HPV self-sampling will have higher uptake than referrals to off-site screening. (arm 3 vs arm 2)

Hypothesis 4.3: Referral to off-site screening following participation in an educational session on cervical cancer will result in higher screening coverage compared to current practices. (arm 2 vs arm 1)

Hypothesis 4.4: Uptake of off-site screening among those who refuse the self-sampling in arm 3 will be lower than uptake of off-site screening in arm 2

Objective 5: Examine the impact of HPV self-sampling on follow-up testing and care

Hypothesis 5.1: Women whose on-site HPV testing came out positive will go for follow-up testing and care

Objective 6: Assess the **feasibility** of the information session and the self-sampling test

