5.1. Arm1

We will contact the respective instances in each study country to ask if more detailed data are available on screening coverage of the target group of socio-economically vulnerable women.

Outcome measures that will be examined for arm 1 are:

- Screening coverage at national level
- Screening coverage in the respective research area in each study country
- Follow-up rate among women who test positive (i.e. have a positive pap smear)

5.2. Arm 2 and arm 3

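### Arm 1 is a below-national, hard-to-reach rate in Hypothesis 2.1 but the national programme in Objective 4 and section 6.1, and no single comparator is named for the arm 1 contrasts

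*Protocol*

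**What the plan says.** Arm 1 is not recruited. It is a set of coverage rates obtained from outside bodies, and it is the comparator for Hypothesis 4.1 (arm 3), Hypothesis 4.3 (arm 2) and Take-up 1 (arm 3). The protocol describes it in these ways:

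- **Section 3.2, Hypothesis 2.1:** "uptake of cervical cancer screening among the participants will be lower than the national average (but similar to results found in arm 1".
- **Section 3.2, Objective 4:** "Compare the uptake of the on-site HPV testing (arm3) with the current national screening services (arm1".
- **Section 6.1, primary endpoint:** "defined in Arm 1 as the proportion of women who had a PAP smear taken by a GP or gynaecologist within the national screening program".
- **Section 6.1, Take-up 1:** the comparison is "with the current national screening services accounting for self-selection of women who decide to attend clinics (arm 1 vs. arm 3".
- **Section 3.1:** the arm 1 outcomes include national coverage and also "Screening coverage at local level/in hard-to-reach communities". The introductory sentence puts particular weight on hard-to-reach women.
- **Section 5.1:** the team will "ask if more detailed data are available on screening coverage of the target group". The two listed coverage outcomes are national coverage and coverage in each country's research area.

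Hypotheses 4.1 and 4.3 refer only to standard or current practice and name no population.

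**The concern.** Arms 2 and 3 enrol socio-economically vulnerable women through community organisations (sections 4.1 and 4.2.1). Hypothesis 2.1 itself expects these women to be screened less than the national average. If arm 1 is the national rate, its contrasts with arms 2 and 3 contain two things: what the intervention did, and how far these women stood below the nation before it began. The second could hide or shrink a real gain.

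Both rates are to be collected before the study starts (section 3.1). If neither is named as the comparator, the choice stays open until the arm 2 and arm 3 results are known. This affects the primary endpoint as used in Hypotheses 4.1 and 4.3 and in Take-up 1.

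Take-up 1 is also described as accounting for self-selection, although arm 1 supplies only an aggregate rate.

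**Working it through.** **Step 1: the passages side by side.**

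| Place in protocol | What arm 1 is |
|---|---|
| 3.2, Hypothesis 2.1 | Similar to participants, who are below the national average |
| 3.2, Objective 4 | National screening services |
| 6.1, primary endpoint | Pap smears within the national programme, among women with no further restriction |
| 6.1, Take-up 1 | National screening services |
| 3.1 | Both national and local or hard-to-reach coverage |
| 5.1 | Both national and research-area coverage; target-group data requested |

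Hypothesis 2.1 says that participants are below national and that participants are close to arm 1. So arm 1 there is below national and cannot be the national rate. The other entries in section 3.2 and those in section 6.1 do not carry that restriction.

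**Step 2: when the choice matters.** Let N be national coverage, H hard-to-reach coverage and T the take-up in arm 3 (or arm 2), with H < N as Hypothesis 2.1 implies.

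- Against national: T - N
- Against hard-to-reach: T - H
- Change in the estimate from switching comparator: (T - H) - (T - N) = N - H

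The estimate always shifts by N - H. Its sign changes only if H < T < N.

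**Step 3: illustration.** The protocol has no figure to reproduce here: it gives no hard-to-reach rate, no expected take-up and no sample size. National rates are from section 2 (Belgium 55%, Portugal 70.7%, Brazil below 70%, Ecuador 9 to 20%). H is assumed. T is deliberately placed midway between H and N, so the table shows the reversal case. For scale, n = 200 is assumed and clustering is ignored: z = (T - p) / sqrt(p(1 - p)/n), with p = N or H.

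| Country | N % | H % (assumed) | T % (assumed) | T - N | T - H | z v N | z v H |
|---|---|---|---|---|---|---|---|
| Belgium | 55 | 50 | 52.5 | -2.5 | +2.5 | -0.71 | +0.71 |
| Belgium | 55 | 45 | 50 | -5 | +5 | -1.42 | +1.42 |
| Belgium | 55 | 35 | 45 | -10 | +10 | -2.84 | +2.96 |
| Portugal | 70.7 | 50.7 | 60.7 | -10 | +10 | -3.11 | +2.83 |
| Brazil (upper bound) | 70 | 50 | 60 | -10 | +10 | -3.09 | +2.83 |
| Ecuador (upper end) | 20 | 10 | 15 | -5 | +5 | -1.77 | +2.36 |

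Third Belgian row in full: sqrt(0.55 × 0.45/200) = 0.0352 and -0.10/0.0352 = -2.84; sqrt(0.35 × 0.65/200) = 0.0337 and +0.10/0.0337 = +2.96.

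**Step 4: when it does not reverse.** Keep Belgium at N = 55 and H = 35. With T = 65 the differences are +10 and +30; with T = 30 they are -25 and -5. The direction agrees in both cases, and the size still differs by 20 points.

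**The case against.** The strongest defence is that the national services or programme may name a delivery route, a Pap smear by a GP or gynaecologist, and not a population. Section 6.1 says simply women for all three arms, although arms 2 and 3 plainly consist of hard-to-reach women, and section 3.1 gives arm 1 a hard-to-reach focus. On that reading the sections could agree. It is a possible reading, so it would go too far to say that section 6.1 definitely prescribes the general population. It does not settle the matter, because sections 3.1 and 5.1 list national-level coverage as an arm 1 outcome in its own right and never say which rate is compared.

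Other parts of the defence stand:

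- A reader might infer that the verdict on Hypotheses 4.1 and 4.3 will reverse with the comparator. The documents do not support this. The hard-to-reach rate and the take-up are unknown, the reversal needs take-up between the two rates, and in Ecuador that means take-up below 20% at most.
- A reader might infer that section 5.1 drops the hard-to-reach figure in favour of the research area. It still opens with the target group, and section 3.1 already included a local figure.
- A reader might infer that self-selection cannot be handled at all. A method could sit in a statistical analysis plan that is not available here, and questionnaire 1 collects socio-demographics and screening history. What stands is that the protocol makes the claim and names no method.
- The randomised comparison of arm 2 with arm 3 (Hypothesis 4.2, Take-up 2) does not use arm 1.

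**Conclusion.** The inconsistency is in the protocol's own text and goes beyond detail that an analysis plan would supply: the protocol describes the arm 1 side of its primary endpoint in ways that do not fit together. On the plain reading of section 6.1, the arm 1 contrasts carry a bias equal to the gap between national and hard-to-reach coverage. The documents support the direction of that gap, through Hypothesis 2.1, but not its size.

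With an assumed 20-point gap and take-up midway, the Belgian result is -10 points against one rate and +10 against the other. With a 5-point gap the sign still flips, but neither comparison reaches |z| = 1.96 at the assumed n of 200. Outside the interval between the two rates the direction does not depend on the choice. The problem is confined to Hypotheses 4.1 and 4.3 and Take-up 1.

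**What to change.** In section 6.1, Objective 4 and Hypotheses 4.1 and 4.3, and before results are known:

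1. Name one primary arm 1 comparator: coverage among hard-to-reach (socio-economically vulnerable) women in each country. This matches Hypothesis 2.1.
2. State research-area coverage as the single second choice where the agencies hold no target-group figure.
3. Report national coverage as context.
4. Use the participants' screening in the last 3 years, from questionnaire 1 (section 5.2.2.1), only as a labelled sensitivity comparison. If it has to stand in for arm 1 in a country, drop the part of Hypothesis 2.1 that expects similarity to arm 1 there, because it would hold by construction. State also that the measure is self-reported, covers a 3-year window and comes from attendees, whereas arm 3 take-up is a single on-site acceptance.
5. Because arm 1 is an aggregate rate and arm 3 take-up is counted among session attendees, do not claim that Take-up 1 accounts for self-selection unless an adjustment method is specified.

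The cost is protocol wording; questionnaire 1 already collects the sensitivity figure. The downside is small: target-group rates may be less precise than national ones, or unavailable in some countries.
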